## **15. Appendix 2: Patient Interview Guide (at 6 months)**

### **IDI Interview Guide for patients, Interview 2 (at six months)**

Thank you for agreeing to speak with me today. I'd like to talk with you today about your experiences since we spoke together last time.

1. To begin, can you talk about how it was after you left the hospital. If possible, try to remember back to the first few weeks following your return from the hospital in \_\_\_\_ (name month). Tell me how you were feeling just after you returned home.
  - a. Can you talk about your energy levels when you first got home?
  - b. How about your levels of pain?
  - c. Can you talk about the medications you were prescribed? Can you describe what you were prescribed and what you took?
    - i. (if prescribed new drugs) Can you talk about how the medications made you feel?
  - d. Can you talk about who in your home or community (family, friends/neighbors) helped you with your recovery process after discharge?
    - i. How did they help you?
2. Now I'd like to ask you about any healthcare you have received since discharge, if any.
  - a. Can you describe in detail any follow-up visits to hospital/clinic you have had since discharge? **(IF they have followed-up, then ask: )**
    - i. What? Where? When since discharge? How many? For what purpose? (INTERVIEWER – note how /what compares to the advice they received)
    - ii. How have these appointment(s) gone?
    - iii. Have you received any support for these follow-ups? (Family, CHWs)
    - iv. What has been good about these appointment(s)?
    - v. What has been difficult about these follow-ups?
    - vi. Are you facing any challenges with continuing to follow-up visits for your care? Can you talk about these? (Probe on logistics, healthcare setting, finances since discharge, family, community)
    - vii. Some people are told to take different medications after discharge. Have you had any experience with that and if yes how is that going?
    - viii. After being discharged, can you describe where have you been collecting your drugs?
      1. If referred back to your clinic, how has your experience been with that?
  - b. **(IF they have not had any interaction with healthcare system since discharge)** Can you talk about the reasons that you have not seen anyone/gone to a clinic since you left the hospital?
    - i. (IF mentions any challenges – probe A LOT) Can you talk about any barriers or challenges you experienced with follow-ups after discharge?
      1. ? (Probe on logistics, healthcare setting, finances since discharge, family, community)
    - ii. (IF mentions that it is not necessary – probe – this is a misunderstanding)

- iii. (If mentions that they have an appointment booked, then ask): Do you think there will be any challenges for you with getting to this appointment? Can you talk about those challenges?
  - iv. (If they missed the appointment) – Can you talk about the reasons you were unable to make the appointment? (PROBE on what's next)
- 3. Now I'd like to ask you more about your relationship with the CHW who supported you following discharge.
  - a. Can you talk about the different ways the CHW supported your recovery, if at all? Let's list these. Phone calls? Visits? What else?
  - b. Can you talk about which of these ways helped you the most?
    - i. Are there any things that you were able to do (care you were able to receive, medications you were able to access) that you may not have been able to do/get without support from the CHW?
    - ii. How did the CHW support your follow-up visit with the hospital, if at all?
    - iii. How did the CHW support your follow-ups with your clinic, if at all?
  - c. Which of these things helped you the least, or you would have preferred they had not?
    - i. Can you talk about anything the CHW did that you did not appreciate or find useful or helpful?
  - d. What else would you have appreciated from the CHW? How else would you have liked them to help you?
    - i. If you could go back in time to when you were in the hospital, is there anything you would have liked to have gone differently that you think would have helped you to recover faster or to get better?
- 4. (for those who screened for mental health/alcohol). I believe we referred you for additional care with (Strong Minds / \_\_\_\_ alcohol care).
  - a. Can you talk about what happened after you received the referral?
  - b. Can you talk about any visits you had to (Strong minds / \_\_\_\_ ).
  - c. Can you talk about your experience there? What did you learn? How did it make you feel?
  - d. Can you talk about what has happened, if anything, since your first visit?
- 5. What would you say is the biggest change or the most significant and positive thing that has happened for you as a result of this program (support from CHWs)?
  - a. What makes you say that?
- 6. Can you talk about any changes that have taken place for you in the last six months?
  - a. Disclosure? – any changes in who knows your status?
  - b. Behavioral health – any changes in behaviors that might be risky? (e.g., alcohol)
  - c. Relationships – any changes in your personal relationships with family members?
  - d. Self-esteem – Any changes in how you feel about yourself?
- 7. We are going to try to build up this program to support more patients like you who are leaving the hospital to help support them to recover.
  - a. Can you think of any recommendations you have for us that could help to make this support program stronger?
  - b. What do you think are the things that you need in order to get better?
  - c. What does your family need in order to be able to support you to get better?

- d. In addition to medical advice and treatment, what additional form of support do you need to stay/get healthy? ( e.g., Nutrition , information, psychological, financial, religious )
- e. What are all the challenges you are facing now to stay/get healthy?
  - i. With treatment, clinic, or access to healthcare
  - ii. With family or support
  - iii. With finances following hospital stay
  - iv. Within community or its expectations
  - v. Others? (Probe on those related to ART and ART use, especially cost of healthcare -transportation, labs, tests, medicines)
  - vi. What is it that you think should be done to help you overcome these challenges?
- f. What kinds of support are you receiving? And from where? Whom?

## **16. Appendix 3: Caregiver Interview Guide**

### **Interview with Care Giver**

IDI Interview Guide for Caretakers of Patients – End line

When appropriate, please make sure you collect this information from the participant.

- Community name:
- Age:
- Gender:
- Education level
- Religion

***NOTE: We will need to develop coding scheme to link caretaker to patient for transcription purposes.***

1. (Rapport building) First, tell me about yourself and your family in your household.(Children? Dependents?)
  - a. Tell me a little bit about how you are related to \_\_\_\_\_?
  - b. Tell me about the role you play in this household?
  - c. What kind of work do you do? (If lives in different household from patient, then ask: Tell me a bit about how people in this household get by, what are the different kinds of work they do?)

**(Transition to new topic)**

**We recently talked to \_\_\_\_\_ and we would like to talk to you about your role since their hospitalization.**

2. First could you please talk about the events that led to \_\_\_\_\_'s hospitalization in \_\_\_\_\_ [month]?
  - a. What, in your mind, were the reasons that \_\_\_\_\_ got sick and needed to be hospitalized?
  - b. Has he/she ever been hospitalized before this? How many times in the past has this happened?
    - i. **If yes**, what are the reasons \_\_\_\_\_ has been hospitalized in the past?
3. What role did you play in looking after \_\_\_\_\_ when \_\_\_\_\_ was in the hospital? (**IF bedside, or there often, then ask following**):
  - a. What was the discharge process like? Can you talk about how you learned when \_\_\_\_\_ was going to be discharged? (PROBE: sudden, knew a few days in advance?)
  - b. How did you feel about \_\_\_\_\_ being discharged when they were? (Early? Late? From their perception)
  - c. Can you talk about the advice the doctors/nurses gave \_\_\_\_\_ about what he was supposed to do following discharge?
    - i. What exactly do you remember about this?

- ii. Was \_\_\_\_\_ given any referral to a local clinic?
- iii. How did you feel about the advice/instructions you were given? (easy to understand, not feasible, helpful, unhelpful, etc.)
- iv. Was \_\_\_\_\_ given any medicine from the hospital? Was there any that you were asked to buy because the hospital did not have?

4. Let's talk about what it's been like since \_\_\_\_\_ returned home after the last hospitalization. How has that been for you?

- a. What is going well for you and for \_\_\_\_\_ so far?
- b. Can you talk about any follow-up for clinic care, appointments \_\_\_\_\_ has attended since coming home?
- c. **(if got care)** Can you describe the role you played in getting \_\_\_\_\_ to the hospital/clinic for their follow-up care appointments?
  - i. Can you describe whether \_\_\_\_\_ received any new medication or treatment recommendations since discharge? If so – how has it been to support \_\_\_\_\_'s medication/treatment adherence?
- d. **(If has not followed-up)** Can you talk more about the reasons that \_\_\_\_\_ has not had a follow-up visit yet?
  - i. What challenges have you faced with supporting \_\_\_\_\_ to follow-up with care since leaving the hospital?
    - 1. Hospitalization can be expensive. Can you talk about any of the impacts of those costs for you and your family?

5. What other challenges have you had in caring for \_\_\_\_\_? (Time, resources, types of treatment).

- a. Challenges
  - i. Individual level – lack of emotional support, over burden, lack of information/knowledge, uncooperative patient
  - ii. Household level – Relationship dynamics, financial challenges
  - iii. Community level – stigma, people in the community asking questions
- b. How do these challenges you face affect/influence how \_\_\_\_\_ takes his/her treatment?

6. How would you like \_\_\_\_\_ to be getting care? What do you think \_\_\_\_\_ needs to get better?

- a. What kind of advice do you give( name of the patient) to help him/her stay healthy?
- b. What kind of support do you wish you had to better support( name of the patient)
- c. What would you like to see happen differently that can help ..... To stay healthy?
- d. What else could help you to be able to address those challenges, or what would need to happen to help remove those challenges?

7. Now I'd like to ask you more about your relationship with the CHW who supported \_\_\_\_\_ following discharge.

- a. Can you talk about the different ways the CHW supported \_\_\_\_\_ recovery, if at all? Let's list these. Phone calls? Visits? What else?
- b. Can you talk about which of these ways helped \_\_\_\_\_ and you the most?

- i. Are there any things that you were able to do (care you were able to receive, medications you were able to access) that you may not have been able to do/get without support from the CHW?
- ii. How did the CHW support \_\_\_\_ follow-up visit with the hospital, if at all?
- iii. How did the CHW support \_\_\_\_ follow-ups with your clinic, if at all?
- c. Which of these things helped \_\_\_\_ the least, or you would have preferred they had not?
  - iv. Can you talk about anything the CHW did that you did not appreciate or find useful or helpful?
- d. What else would you have appreciated from the CHW? How else would you have liked them to help \_\_\_\_?
  - v. If you could go back in time to when \_\_\_\_ was in the hospital, is there anything you would have liked to have gone differently that you think would have helped \_\_\_\_ to recover faster or to get better?

8. What would you say is the biggest change or the most significant and positive thing that has happened for \_\_\_\_ as a result of this program (support from CHWs)?

- a. What makes you say that?

9. Can you talk about any changes that have taken place for \_\_\_\_ in the last six months?

- a. Disclosure? – any changes in who knows \_\_\_\_ status?
- b. Behavioral health – any changes in behaviors that might be risky? (e.g., alcohol)
- c. Relationships – any changes in \_\_\_\_ personal relationships with family members?
- d. Self-esteem – Any changes in how \_\_\_\_ feels about themselves?

10. We are going to try to build up this program to support more patients like \_\_\_\_ who are leaving the hospital to help support them to recover.

- a. Can you think of any recommendations you have for us that could help to make this support program stronger?
- b. What do you think are the things that you need in order to get better?
- c. What does your family need in order to be able to support you to get better?
- d. In addition to medical advice and treatment, what additional form of support do you need to stay/get healthy? ( e.g., Nutrition , information, psychological, financial, religious )
- e. What are all the challenges you are facing now to stay/get healthy?
  - vi. With treatment, clinic, or access to healthcare
  - vii. With family or support
  - viii. With finances following hospital stay
  - ix. Within community or its expectations
  - x. Others? (Probe on those related to ART and ART use, especially cost of healthcare -transportation, labs, tests, medicines)
  - xi. What is it that you think should be done to help you overcome these challenges?
- f. What kinds of support are you receiving? And from where? Whom?

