### **2.2 Rationale**

Many PLHIV have poor outcomes following hospitalization, including high mortality, readmission, and gaps in HIV care engagement. This is likely multi-factorial and not all etiologies may be modifiable. While high mortality may be due to incurable cancer, the majority of deaths in PLHIV are thought to be caused by infectious diseases for which treatments exist. However, succumbing to these life-threatening infections after discharge may be due to poor understanding of discharge instructions, lack of post hospital care, and poor understanding of required follow up. Psychosocial support also plays a role in the mental and physical health of these sick patients.

In ReCharge 1, we gathered formative data and identified at least three major factors that undermine HIV clinical outcomes after hospital discharge. First, there are gaps in continuity of care between the discharging facility and outpatient. Second, support from family is often suboptimal due to lack of understanding on the cause of illness, lack of HIV status disclosure, and the cost of care. Third, HIV comorbidities may underpin or complicate the immediate reason for discharge or the post-discharge engagement in care. These data were disseminated to local experts in Zambia including from the Ministry of Health and used to create a new care model for post-discharge HIV care. The care model draws from other successful programs in Zambia. In ReCharge 2 we now propose to pilot the program and assess feasibility, acceptability, and potential for clinical impact.

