### 6.3 Participant inclusion and exclusion criteria

- Hospitalized patients living with HIV soon to be discharged (n=100)
  - Inclusion criteria: (i) age 18+ years, (ii) HIV-positive, (iii) hospitalized for at least 1 night at study site, (iv) clinically stable and expected to be discharged according to their clinician, and (v) objective evidence of suboptimal HIV outcome, defined as HIV VL above the lower limit of the assay or CD4 count <=200.
  - Exclusion criteria: (i) unable to provide informed consent, (ii) no phone, (iii) planning to reside outside of Lusaka urban district after discharge
- Health systems leaders for one-on-one key informant interviews (around n=6):
  - Inclusion criteria: (i) age 18+ years old, (ii) experienced administrators and clinical heads in Zambia, and (iii) professional experience at UTH or another health facility in Lusaka
  - Exclusion criteria: (i) declines to participate.
- CHWs providing ReCharge intervention, for interviews (n=4-8):

- Inclusion criteria: (i) age 18+ years old, (ii) HIV peer educator or psychosocial counselor, and (iii) at least 2 years of experience supporting HIV care uptake at the community-level
- Exclusion criteria: (i) declines to participate.
- Caretakers of patients living with HIV who received the ReCharge intervention (up to 20)
  - Inclusion Criteria: (i) age 18+ years old, (ii) serves as primary caretaker for participant-patient, (iii) resides with patient the majority of the time
  - Exclusion criteria: (i) patient does not permit inviting caretaker to participate, (ii) declines to participate

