### **9.4 Voluntary participation**

During recruitment and implementation of IDIs, we will counsel participants that their participation is voluntary and regardless of the data they provide, their position with MoH, UTH, etc. will not be impacted in any way. Transcripts will be stripped of identifying information. We will approach patients who are eligible to participate in a discrete manner to maintain confidentiality. We are aware that private space is minimal in AMEU and the inpatient units and our staff will be coached on how to discuss sensitive issues in the most discrete ways possible to avoid inadvertent disclosure. If possible, a private space will be used for consenting and collection of data. When interviewees are conducted away from the hospital either at home or any other space, they will be conducted with consultation with the patient.

Potential participants will be counseled that they can refuse to participate in the study and still receive HIV care at the treatment site. Participants will be free to not answer questions

that they deem too personal during the study. Providers will be highly trained and will receive specific training in human subjects research. The study staff obtaining consent and collecting data will be highly trained in human subjects and responsible conduct of research and will have the appropriate certifications (e.g., NIH).

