**ONLY ASK IF STATUS OF PATIENT IS KNOWN**

**If it's okay, I would like to ask you some questions about \_\_\_\_'s status and your struggles and efforts to support \_\_\_\_ with this.**

1. First, can you tell me when/how you learned about \_\_\_\_'s HIV status? How was that experience for you? (Stigma, fear, friends/family response, reaction)
  - a. How has \_\_\_\_'s HIV status affected your life in this family?
    - i. PROBE: has this had any effect on your relationship within your family?
  - b. Can you talk about whether \_\_\_\_'s status has had any impact on your role in the community? What about \_\_\_\_'s role in the community?
2. What form of treatment has \_\_\_\_ been getting since diagnosis, to your knowledge?
  - a. What is it that has worked well for \_\_\_\_ with the treatment he/she is taking?
  - b. What has not been working well? (type or combination of drugs, changing from first line to second line treatment, taking tuberculosis treatment too, etc.)
3. Now I would like to talk to you about access to care for (name of the patient).
  - a. Where did \_\_\_\_ access his/her care from? Can you talk about any changes in how \_\_\_\_ accessed care over time?
  - b. Apart from getting care from the clinic, are there other places and forms of treatment where \_\_\_\_ got care?
    - i. Probe about traditional medicine, faith healing.
    - ii. How has this affected his/her journey on treatment?
  - c. What, if anything, seemed to work well for \_\_\_\_'s HIV care?
  - d. What did you encourage \_\_\_\_ to do? What did others encourage \_\_\_\_ to do?
4. **(If the patient learned their HIV status before hospitalization):** Many people have a difficult time accessing and staying in HIV care or on treatment. For many, the challenges they face with staying on ART lead them to be unable to take treatment every day or even stop taking it. Can you describe any experiences \_\_\_\_ has had with this?
  - c. Can you talk about any challenges \_\_\_\_ faced with taking ART?
    - i. Challenges at home/In household? Community?
    - ii. Concerns with taking it because of advice received (from family, friends, church)
    - iii. Challenges with clinic / accessing drugs? (Stigma, time, cost, distance, rude staff)
    - iv. Challenges/barriers within yourself (acceptance of status, motivation, beliefs, fears, side-effects, what others might think etc.)

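### Two caregiver-guide prompts, on who knows the patient's status and on ART, sit outside the block restricted to caregivers who know, so an interview could cue one who does not

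*Combined protocol and SAP*

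**What the plan says.** Section 6.3 admits a caregiver who is an adult and who "serves as primary caretaker for participant-patient, (iii) resides with patient the majority of the time". The exclusions are "patient does not permit inviting caretaker to participate, (ii) declines to participate". Neither list mentions knowledge of the patient's HIV status.

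The caregiver guide (Appendix 3) is used at endline. Items 1 to 10 come first and are followed by a block headed "ONLY ASK IF STATUS OF PATIENT IS KNOWN". Within items 1 to 10:

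- Item 9 asks about changes for the patient over the last six months. Its first prompt, 9a, is labelled as being about disclosure and asks about "any changes in who knows" the patient's status.
- Item 10e asks about current challenges to health. Its sub-item (x) carries an interviewer note: "Probe on those related to ART and ART use".

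Neither prompt has a skip instruction.

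Section 2.2 lists "lack of HIV status disclosure" among the reasons why family support was found wanting in the formative work. Section 4.4 counts, as a feasibility endpoint, the patients who have disclosed to a treatment supporter. Section 9.4 says that staff will be coached to "avoid inadvertent disclosure", in a passage about scarce private space on the wards. Section 9.3.1 treats loss of confidentiality as a minimal risk, handled by coded and de-identified data.

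**The concern.** The guide recognises that a caregiver may not know the patient's status and protects that situation in its last block. Two earlier prompts touch the same subject without that protection. A caregiver who does not know, and who is asked about disclosure of the patient's status and then about ART, may work out what the patient has chosen not to say.

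Such a disclosure cannot be undone. It would be caused by the study and not by the patient's care, and coding or de-identifying the data cannot prevent it. It could also disturb the family support and retention that the pilot sets out to observe.

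**Working it through.** No arithmetic applies. The check sets the eligibility text, the order of the guide and the stated safeguards side by side.

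1. **Can an uninformed caregiver be interviewed?** Yes. Section 6.3 selects on age, role and co-residence and excludes on patient refusal or caregiver refusal. Section 5.3.2 and section 6.4 (item 4) add consent steps but no check on what the caregiver knows.

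2. **Do the authors allow for such caregivers at endline?** Yes. The heading of the restricted block would serve no purpose in an endline guide if every caregiver knew. Section 4.4 likewise treats disclosure as a proportion to be measured.

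3. **Are the two prompts covered by the restriction?** No. Items 9a and 10e(x) precede the heading, which governs only what follows it.

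4. **Is the missing condition just the guide's style?** No. Appendix 3 uses conditions elsewhere: item 3 has follow-ups only for caregivers who were at the bedside or there often, and items 4c and 4d depend on whether the patient received follow-up care. A likely source of the gap is visible. Items 9 and 10 closely track items 6 and 7 of the six-month patient guide (Appendix 2), whose respondents know their own status.

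5. **Does a stated safeguard close the gap?**
   - Patient permission (sections 5.3.2, 6.3 and 6.4) covers the invitation. It does not record what the caregiver knows or limit what is asked.
   - Section 9.4 deals with discretion where private space is short. It does not extend to the content of caregiver interviews.
   - Section 9.3.1 relies on codes and de-identified data, which do not bear on a spoken question.
   - Section 5.3.2 also plans caregiver interviews after a patient's death, with up to 4 expected. It does not say how the patient's permission or disclosure wishes would then be established.

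6. **How many caregivers are involved?** Section 8.1.2 plans 16 caregiver interviews and section 6.3 allows up to 20. These figures are ceilings on the number who could be affected. The documents give no figure for the share who would be uninformed, so no count is estimated.

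**The case against.** There is a fair case that the risk is modest.

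- **The interviewer will often know already.** Under section 5.3.2 the same interviewer sees the patient twice and then seeks permission and interviews the caregiver. Appendix 1 (item 2b) asks whom the patient has told, and Appendix 2 (item 6a) asks about changes since. This stands, and it makes the fix easier. But nothing tells the interviewer to use that information at items 9a and 10e(x), and a patient who has died has no six-month interview.
- **The patient can refuse the invitation.** This stands as a way to lower the number at risk. Permission to invite is still not a statement that the caregiver knows.
- **Some caregivers will have learned by endline.** Section 5.1 has the CHW counsel patient and caregivers on why each medicine was prescribed, ART included. This also stands, and it means that the formative finding in section 2.2 cannot be carried straight over to endline. The restricted block shows that the authors do not assume everyone is informed.
- **The wording is indirect.** Item 9a says *status*, not *HIV status*, and the ART phrase is a note to the interviewer, not text to read out. This stands: disclosure may or may not follow.
- **Appendix 8 was not available for review.** It may name HIV or contain a check of its own. Nothing can be inferred from it either way. If it names HIV, it would itself be the main route of disclosure and reordering the prompts would achieve less.

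A reader might infer that the guide contradicts section 9.4. It does not: that passage concerns privacy on the wards, and the most that can be said is that it stops short of caregiver interviews. A reader might also infer that every uninformed caregiver would learn of the HIV infection. The indirect wording does not support that.

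**Conclusion.** The point holds as a gap in the interview guide that carries a confidentiality risk. The plan permits interviews with caregivers who do not know the patient's HIV status, and two prompts on that subject come before the guide's own restriction and without a condition. An interviewer following the guide could inadvertently cue such a caregiver.

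The size is unknown. It is bounded above by the number of caregivers interviewed, and existing features of the plan probably keep it well below that bound. The conclusion assumes that the guide is followed in its printed order and that Appendix 8 does not already screen for knowledge of status. A demonstrated harm or a stated number of disclosures would go beyond what the documents show. The correction is still worth making, because an unwanted disclosure is irreversible and the change is nearly free.

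**What to change.** - In Appendix 3, move item 9a and the ART note in item 10e(x) into the block for caregivers who know the status, or repeat that block's condition on each of them.
- In section 5.3.2 or 6.3, add a step when the patient's permission is sought: record whether the caregiver knows the HIV status, drawing on what the patient interviews already collect.
- Ask only the neutral items when the answer is no or unknown. Apply the same rule when the patient has died and no answer was recorded.
- Check that Appendix 8 is consistent with this.

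The cost is two relocated prompts and one recorded answer per caregiver. The analysis loses disclosure and ART responses from uninformed caregivers, who could not answer those prompts meaningfully in any case.
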